15 ETHICS

15.1 Institutional Review Board (IRB) Approval

The final study protocol and the final version of the informed consent form must be approved in writing by an IRB. The site investigator must submit written approval by the IRB to HCRN before he or she can enroll subjects into the study.

The site investigator is responsible for informing the IRB of any amendment to the protocol in accordance with local requirements. In addition, the IRB must approve all advertising used to recruit subjects for the study. The protocol must be re-approved by the IRB, as local regulations require.

Progress reports and notifications of serious and unexpected adverse events will be provided to the IRB according to local regulations and guidelines.

15.2 Ethical Conduct of the Study

The study will be performed in accordance with ethical principles originating from the Declaration of Helsinki. Conduct of the study will be in compliance with ICH Good Clinical Practice, and with all applicable federal (including 21 CFR parts 56 & 50), state, or local laws.

15.3 Informed Consent Process

The site investigator will ensure the subject is given full and adequate oral and written information about the nature, purpose, possible risks and benefits of the study. Subjects must also be notified they are free to discontinue from the study at any time. The subject should be given the opportunity to ask questions and allowed time to consider the information provided.

The subject's signed and dated informed consent must be obtained before conducting any procedure specifically for the study. The site investigator must store the original, signed informed consent form. A copy of the signed informed consent form must be given to the subject.

11. APPENDICES

11.1 Appendix 1. Concomitant Medications to Avoid

Examples of sensitive *in vivo* CYP substrates and CYP substrates with narrow therapeutic range are summarized below.

Examples of substrates that may be affected by entinostat

CYP Enzymes	Substrates with narrow therapeutic range ¹
CYP1A2	Theophylline, tizanidine
CYP2C8	Paclitaxel
CYP3A ²	Alfentanil, astemizole ³ , cisapride ³ , cyclosporine, dihydroergotamine, ergotamine, fentanyl, pimozide, quinidine, sirolimus, tacrolimus, terfenadine ³
1	CYP substrates with narrow therapeutic range refers to drugs whose exposure-response relationship indicates that small increases in their exposure levels by the concomitant use of CYP inhibitors may lead to serious safety concerns (e.g., Torsades de Pointes).
2	Because a number of CYP3A substrates (e.g., darunavir, maraviroc) are also substrates of P-gp, the observed increase in exposure could be due to inhibition of both CYP3A and P-gp.
3	Withdrawn from the United States market because of safety reasons.

P-gp Inhibitors and Inducers

Inhibitors	Inducers
Amiodarone, azithromycin, captopril, carvedilol, clarithromycin, conivaptan, diltiazem, dronedarone, felodipine, lopinavir, quercetin, ranolazine, ticagrelor, ritonavir, cyclosporine, verapamil erythromycin, ketoconazole, itraconazole, quinidine	Avasimibe, carbamazepine, phenytoin, rifampin, St John's Wort, tipranavir/ritonavir

Gastric Acid Reducing Drugs

Proton Pump Inhibitors	
 Omeprazole (Prilosec, Zegerid) Lansoprazole (Prevacid) Rabeprazole (AcipHex) Pantoprazole (Protonix) Esomeprazole (Nexium)
H2 Inhibitors	
 Cimetidine (Tagamet) Ranitidine (Zantac) Famotidine (Pepcid) Nizatidine (Axid)
Antacids	
 Alka-Seltzer Alka-2, Surpass Gum, Titrалac, Tums Milk of Magnesia Alternagel, Amphojel Gaviscon, Gelusil, Maalox, Mylanta, Rolaids Pepto-Bismol

Information obtained from the following website: Gastric acid reducing drugs: <http://www.everydayhealth.com/ulcer/ulcer-treatment.aspx>

11.2 Appendix 2. Nivolumab and Ipilimumab Adverse Event Management Algorithms

These general guidelines constitute guidance to the site Investigator and may be supplemented through discussions with the Sponsor-Investigator by contacting the BTCRC project manager. The guidance applies to all immuno-oncology agents and regimens.

As general principle, differential diagnoses should be diligently evaluated according to standard medical practice. Non-inflammatory etiologies should be considered and appropriately treated.

[figure not shown]
Corticosteroids are a primary therapy for immuno-oncology drug-related adverse events. The oral equivalent of the recommended IV doses may be considered for ambulatory patients with low-grade toxicity. The lower bioavailability of oral corticosteroids should be taken into account when switching to the equivalent dose of oral corticosteroids.

Consultation with a medical or surgical specialist, especially prior to an invasive diagnostic or therapeutic procedure, is recommended.

The frequency and severity of the related adverse events covered by these algorithms will depend on the immuno-oncology agent or regimen being used.

GI Adverse Event Management Algorithm

Rule out non-inflammatory causes. If non-inflammatory cause is identified, treat accordingly and continue I-O therapy. Opiates/narcotics may mask symptoms of perforation. Infliximab should not be used in cases of perforation or sepsis.

[figure not shown]

Patients on IV steroids may be switched to an equivalent dose of oral corticosteroids (e.g. prednisone) at start of tapering or earlier, once sustained clinical improvement is observed. Lower bioavailability of oral corticosteroids should be taken into account when switching to the equivalent dose of oral corticosteroids.

Updated 05-Jul-2016

Renal Adverse Event Management Algorithm

Rule out non-inflammatory causes. If non-inflammatory cause, treat accordingly and continue I-O therapy

[figure not shown]

Patients on IV steroids may be switched to an equivalent dose of oral corticosteroids (e.g. prednisone) at start of tapering or earlier, once sustained clinical improvement is observed. Lower bioavailability of oral corticosteroids should be taken into account when switching to the equivalent dose of oral corticosteroids.

Updated 05-Jul-2016

Pulmonary Adverse Event Management Algorithm

Rule out non-inflammatory causes. If non-inflammatory cause, treat accordingly and continue I-O therapy. Evaluate with imaging and pulmonary consultation.

[figure not shown]

Patients on IV steroids may be switched to an equivalent dose of oral corticosteroids (e.g. prednisone) at start of tapering or earlier, once sustained clinical improvement is observed. Lower bioavailability of oral corticosteroids should be taken into account when switching to the equivalent dose of oral corticosteroids.

Updated 05-Jul-2016

Hepatic Adverse Event Management Algorithm

Rule out non-inflammatory causes. If non-inflammatory cause, treat accordingly and continue I-O therapy. Consider imaging for obstruction.

Patients on IV steroids may be switched to an equivalent dose of oral corticosteroids (e.g. prednisone) at start of tapering or earlier, once sustained clinical improvement is observed. Lower bioavailability of oral corticosteroids should be taken into account when switching to the equivalent dose of oral corticosteroids.

[figure not shown]
*I-O therapy may be delayed rather than discontinued if AST/ALT \leq 8 x ULN or T.bili \leq 5 x ULN.

**The recommended starting dose for grade 4 hepatitis is 2 mg/kg/day methylprednisolone IV.

Updated 05-Jul-2016

Endocrinopathy Management Algorithm

Rule out non-inflammatory causes. If non-inflammatory cause, treat accordingly and continue I-O therapy. Consider visual field testing, endocrinology consultation, and imaging.

[figure not shown]

Patients on IV steroids may be switched to an equivalent dose of oral corticosteroids (e.g. prednisone) at start of tapering or earlier, once sustained clinical improvement is observed. Lower bioavailability of oral corticosteroids should be taken into account when switching to the equivalent dose of oral corticosteroids.

Updated 05-Jul-2016

Skin Adverse Event Management Algorithm

Rule out non-inflammatory causes. If non-inflammatory cause, treat accordingly and continue I-O therapy.

Patients on IV steroids may be switched to an equivalent dose of oral corticosteroids (e.g. prednisone) at start of tapering or earlier, once sustained clinical improvement is observed. Lower bioavailability of oral corticosteroids should be taken into account when switching to the equivalent dose of oral corticosteroids.

[figure not shown]
*Refer to NCI CTCAE v4 for term-specific grading criteria.

[▲]If SJS/TEN is suspected, withhold I-O therapy and refer patient for specialized care for assessment and treatment. If SJS or TEN is diagnosed, permanently discontinue I-O therapy.

Updated 05-Jul-2016

Neurological Adverse Event Management Algorithm

[figure not shown]
Rule out non-inflammatory causes. If non-inflammatory cause, treat accordingly and continue I-O therapy.

Patients on IV steroids may be switched to an equivalent dose of oral corticosteroids (e.g. prednisone) at start of tapering or earlier, once sustained clinical improvement is observed. Lower bioavailability of oral corticosteroids should be taken into account when switching to the equivalent dose of oral corticosteroids.

Updated 05-Jul-2016

Myocarditis Adverse Event Management Algorithm

Patients on IV steroids may be switched to an equivalent dose of oral corticosteroids (eg, prednisone) at start of tapering or earlier, once sustained clinical improvement is observed. Lower bioavailability of oral corticosteroids should be taken into account when switching to the equivalent dose of oral corticosteroids.

Prophylactic antibiotics should be considered in the setting of ongoing immunosuppression.

ATG = anti-thymocyte globulin; BNP = B-type natriuretic peptide; ECG = electrocardiogram; IV = intravenous; MRI = magnetic resonance imaging

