5.6 Supportive Care

Subjects should receive appropriate supportive care measures as deemed necessary by the site investigator.

Suggested supportive care measures for the management of adverse events (AEs) with potential immunologic etiology are outlined below. Where appropriate, these guidelines include the use of oral or intravenous treatment with corticosteroids as well as additional anti-inflammatory agents if symptoms do not improve with administration of corticosteroids. Note that several courses of steroid tapering may be necessary as symptoms may worsen when the steroid dose is decreased. For each disorder, attempts should be made to rule out other causes such as metastatic disease or bacterial or viral infection, which might require additional supportive care. The treatment guidelines are intended to be applied when the investigator determines the events to be related to nivolumab or ipilimumab.

5.6.1 Suggested supportive care measures for the management of AEs that are related to nivolumab or ipilimumab

Immuno-oncology (I-O) agents are associated with AEs that can differ in severity and duration than AEs caused by other therapeutic classes. Nivolumab and ipilimumab are considered immuno-oncology agents in this protocol. Early recognition and management of AEs associated with immuno-oncology agents may mitigate severe toxicity. Management algorithms have been developed to assist investigators in assessing and managing the following groups of AEs: Gastrointestinal, Renal, Pulmonary, Hepatic, Endocrinopathies, Skin, Neurological.

For subjects expected to require more than 4 weeks of corticosteroids or other immunosuppressants to manage an AE, consider recommendations provided in the algorithms. These algorithms are found in Appendix 2. The guidance provided in these algorithms should not replace the site Investigator's medical judgment but should complement it.

Subjects on IV steroids may be switched to an equivalent dose of oral corticosteroids (e.g. prednisone) at start of tapering or earlier, once sustained clinical improvement is observed. Lower bioavailability of oral corticosteroids should be taken into account when switching to the equivalent dose of oral corticosteroids.

Subjects who are started on steroids for management of an immune-related event should not resume immunotherapy until steroids have been tapered to \leq prednisone 10mg daily or an equivalent dose of an alternative corticosteroid.

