6.1 Dose Delays/Dose Modifications

All dose modifications should be based on the AE requiring the greatest modification and should be properly documented in source documents. Investigators may take a more conservative approach than the guidelines outlined below based on clinical judgment that is in the best interest of the subject. **NOTE:** if one or more study drugs are permanently discontinued, subjects may continue with the remaining drugs per protocol at the discretion of the treating physician if the subject is receiving clinical benefit.

For subjects with immune-related adverse events (irAEs), if the management guidelines suggest delay or discontinuation, both nivolumab and ipilimumab should be held or discontinued. In the event that ipilimumab must be permanently discontinued due to an AE which can be directly attributed to ipilimumab (e.g. an infusion reaction), nivolumab may be continued per protocol at the discretion of the treating physician.

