	Grade 4 hyperglycemia	Permanently discontinue
Nephritis and Renal Dysfunction	Serum creatinine more than 1.5 and up to 6 times the ULN	Withhold dose ^a
	Serum creatinine more than 6 times the ULN	Permanently discontinue
Skin	Grade 3 rash or suspected Stevens-Johnson syndrome (SJS) or toxic epidermal necrolysis (TEN)	Withhold dose ^a
	Grade 4 rash or confirmed SJS or TEN	Permanently discontinue
Encephalitis	New-onset moderate or severe neurologic signs or symptoms	Withhold dose ^a
	Immune-mediated encephalitis	Permanently discontinue
Other	Other Grade 3 adverse reaction	
	First occurrence	Withhold dose ^a
	Recurrence of same Grade 3 adverse reactions	Permanently discontinue
	Life-threatening or Grade 4 adverse reaction	Permanently discontinue
	Grade 3 myocarditis	Permanently discontinue
	Requirement for 10 mg per day or greater prednisone or equivalent for more than 12 weeks	Permanently discontinue
	Persistent Grade 2 or 3 adverse reactions lasting 12 weeks or longer	Permanently discontinue

* Toxicity was graded per National Cancer Institute Common Terminology Criteria for Adverse Events. Version 4.0 (NCI CTCAE v4).

^a Resume treatment when adverse reaction improves to Grade 0 or 1.

^b HCC: hepatocellular carcinoma.

^c Resume treatment when AST/ALT returns to baseline.

Dose delay guidelines for ipilimumab related adverse events

Recommendations for nivolumab modifications are below. When nivolumab is administered with ipilimumab, if nivolumab is held then ipilimumab should also be held.

Mild to moderate adverse reactions	Action
Gastrointestinal: Moderate diarrhoea or colitis that either is not controlled with medical management or that persists (5-7 days) or recurs	1. Withhold dose until an adverse reaction resolves to Grade 1 or Grade 0 (or returns to baseline). 2. If resolution occurs, resume therapy. ^d 3. If resolution has not occurred, continue to withhold doses until resolution then resume treatment. ^d 4. Discontinue YERVOY if resolution to Grade 1 or Grade 0 or return to baseline does not occur.
Hepatic: Moderate elevations in transaminase (AST or ALT > 5 to ≤ 8 x ULN) or total bilirubin (> 3 to ≤ 5 x ULN) levels	
Skin: Moderate to severe (Grade 3) ^b skin rash or widespread/intense pruritus regardless of etiology	
Endocrine: Severe adverse reactions in the endocrine glands, such as hypophysitis and thyroiditis that are not adequately controlled with hormone replacement therapy or high-dose immunosuppressive therapy	

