Neurological: Moderate (Grade 2) ^b unexplained motor neuropathy, muscle weakness, or sensory neuropathy (lasting more than 4 days)	
Other moderate adverse reactions^c	

^a No dose reduction of YERVOY is recommended.

^b Toxicity grades are in accordance with National Cancer Institute Common Terminology Criteria for Adverse Events Version 3.0 (NCI-CTCAE v3).

^c Any other organ system adverse reactions that are considered immune-related should be graded according to CTCAE.

^d Decision whether to withhold a dose should be based on severity.

^d Until administration of all 4 doses or 16 weeks from first dose, whichever occurs earlier.

ULN = upper limit of normal

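### For ipilimumab in Cycles 1-4, Section 6.1.3 and Appendix 2 conflict on Grade 3 rash or widespread/intense pruritus with a non-inflammatory cause, and nothing says which governs

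*Combined protocol and SAP*

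**What the plan says.** Two parts of the protocol tell a site what to do with the antibodies after a skin event.

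- **Appendix 2, Skin Adverse Event Management Algorithm.** It begins by asking the site to rule out non-inflammatory causes, then says: "If non-inflammatory cause, treat accordingly and continue I-O therapy". The visible text sets no grade limit on this. Section 5.6.1 makes clear which drugs are meant: "Nivolumab and ipilimumab are considered immuno-oncology agents in this protocol".
- **Section 6.1.3, ipilimumab table.** Under the title "Dose delay guidelines for ipilimumab related adverse events", the skin row covers moderate to severe (Grade 3) "skin rash or widespread/intense pruritus regardless of etiology". The action is to withhold until Grade 0-1 or baseline and then resume. A footnote adds: "Decision whether to withhold a dose should be based on severity".

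Section 6.1.2 allows no dose reduction of ipilimumab and refers the reader to a table for delay or discontinuation. It also says that a dose held for toxicity that cannot be resumed within 48 hours is not made up. Ipilimumab is planned once per 21-day cycle for four cycles (Sections 5.1.1 and 5.4.3).

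**The concern.** One text makes the cause of the rash or itch the deciding fact; the other tells the site to disregard it. Where the cause is non-inflammatory, a site that opens Appendix 2 is told to continue and a site that opens Section 6.1.3 is told to withhold. Two sites could treat the same event differently and each could point to protocol text in support. At stake are consistent handling of a severe skin event during ipilimumab treatment and the ipilimumab exposure actually delivered.

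**Working it through.** This is a comparison of wording. The plan has no figure of its own to reproduce on this point.

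**Step 1. Apply both texts to one case:** a patient in Cycles 1-4 with Grade 3 rash, or widespread/intense pruritus, for which a non-inflammatory cause has been found.

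| | Section 6.1.3, ipilimumab skin row | Appendix 2, skin algorithm, opening line |
|---|---|---|
| Role of cause | None ("skin rash or widespread/intense pruritus regardless of etiology") | Decisive |
| Role of grade | Defines the trigger | None stated in the visible text |
| Ipilimumab | Withhold until Grade 0-1 or baseline | Continue |

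This assumes that the action column, printed beside the first row of the table, applies to every row in that block. The layout suggests so.

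**Step 2. Look for text that settles it.**

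- The table title and a sentence in Section 5.6 refer to events judged related to the antibodies. This could take some events out of scope, but it does not say which text wins for those that remain.
- Section 6.1 bases modification on the adverse event needing the largest change. That ranks events against each other, not two instructions for one event.
- Section 6.1 lets investigators be more conservative. That is a permission, not an order of precedence.
- Section 6.1 also says "if the management guidelines suggest delay or discontinuation, both nivolumab and ipilimumab should be held or discontinued", without saying whether those guidelines are the tables in 6.1.3 or the algorithms in Appendix 2.

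None of these states an order of precedence.

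**Step 3. Size per patient.** Planned ipilimumab doses: 4. One dose held and not made up: 1/4 = 25% of the planned course. This rests on the 48-hour rule in Section 6.1.2. A footnote to the ipilimumab table lets treatment resume until all four doses or 16 weeks from the first dose. If a site read that as allowing a late dose, the effect would be a delay rather than an omission.

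**Step 4. Frequency.** The documents give no rate for Grade 3 rash or intense pruritus with a non-inflammatory cause, so the number of patients affected cannot be calculated.

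**The case against.** **Scope.** The strongest reply is that the table covers only ipilimumab-related events, so a rash with an established non-drug cause never enters it. On that view the words on etiology mean any mechanism within drug-related rash, or they qualify only the pruritus. These readings are possible, and they narrow the conflict. They do not remove it. A drug-related event judged non-inflammatory would still be withheld under the table and continued under the algorithm, and the pruritus-only reading leaves pruritus in conflict. The narrower scope also sits at odds with a row that tells the site to disregard cause.

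**Status.** Appendix 2 calls itself guidance, Section 5.6.1 says the algorithms complement medical judgment, and Section 6.1.2 sends the reader to the table. A site that withholds therefore breaches neither text. That stands. But the tables in 6.1.3 are also introduced as guidelines and recommendations, so the difference in status is not clear enough to act as a precedence rule.

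**What cannot be seen.** The skin algorithm figure is not available here, so any grade-specific limits in it cannot be checked. The footnote on severity cannot be tied with certainty to the skin row, because the table carries two footnotes with the same letter. Both limits stand.

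**Stronger readings that a reader might infer, and that the documents do not support:**

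- *Both antibodies are affected.* The both-drug sentence in Section 6.1 is worded for subjects with immune-related events, which a non-inflammatory event may not be. The other linking rule, in 6.1.3, runs from nivolumab to ipilimumab. The nivolumab skin row withholds for Grade 3 rash but is silent on cause and does not list pruritus. The ipilimumab table's lead-in, "Recommendations for nivolumab modifications are below", repeats the one above the nivolumab table, so its intended reach is uncertain.
- *The DLT count, and so the RP2D, is distorted.* Under Section 5.2.1, Grade 3-4 non-hematological toxicities count only if attributable to study treatment. A rash with a non-drug cause does not itself change the count, and any effect through altered exposure is indirect.
- *A given share of cohorts will be affected.* Any such figure would need an assumed event rate for which the documents offer no basis.

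**Conclusion.** The inconsistency is real for ipilimumab in Cycles 1-4. It is one of wording and precedence; no sample-size or design figure is affected. Its size is up to one of four ipilimumab doses in a patient who has the event, assuming that the hold outlasts the 48-hour limit and that the table's action applies to the skin row. Extension to nivolumab is an open question that the protocol should answer, not an established conflict. Reach is limited: accrual stops after the safety lead-in (at most 18 subjects) and ipilimumab ends after Cycle 4. The correction is still worth making, because it concerns whether a study drug is given after a severe skin event and the present text supports both answers.

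**What to change.** 1. Reconcile the ipilimumab skin row in Section 6.1.3 with the opening instruction of the Appendix 2 skin algorithm, so that a single action is stated for Grade 3 rash or widespread/intense pruritus with a non-inflammatory cause.
2. Say explicitly whether that action applies to nivolumab as well.
3. Add one sentence to Section 6.1 stating which text governs when Section 6.1.3 and Appendix 2 differ.

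The choice of action belongs to the sponsor-investigator and the drug supplier; this review takes no position on it. The cost is wording in the next amendment and a memo to sites, with no added patients or procedures.

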6.1.3 Nivolumab

There are no dose reductions for nivolumab. For toxicity as outlined in this protocol, study therapy should be delayed until the AE improves to the stated level or should be discontinued permanently depending on severity (see table below). If a dose of nivolumab is held for toxicity and cannot be resumed within 48 hours, the dose will not be made up, and the subject will continue to follow the standard dosing schedule. If the dose of nivolumab is held for toxicity and can be resumed within 48 hours, the dose will be given, and the subject will continue to follow the standard dosing schedule (i.e., the next dose will be given on time).

Dose delay guidelines for nivolumab related adverse events

Recommendations for nivolumab modifications are below. When nivolumab is administered with ipilimumab, if nivolumab is held then ipilimumab should also be held.

Adverse Reaction	Severity*	Dose Modification
Colitis	Grade 2 diarrhea or colitis	Withhold dose ^a
	Grade 3 diarrhea or colitis	Withhold dose ^a when administered as a single agent
	Grade 4 diarrhea or colitis	Permanently discontinue when administered with ipilimumab
Pneumonitis	Grade 2 pneumonitis	Withhold dose ^a
	Grade 3 or 4 pneumonitis	Permanently discontinue
Hepatitis/non-HCC ^b	Aspartate aminotransferase (AST) or alanine aminotransferase (ALT) more than 3 and up to 5 times the upper limit of normal (ULN) or total bilirubin more than 1.5 and up to 3 times the ULN	Withhold dose ^a
	AST or ALT more than 5 times the ULN or total bilirubin more than 3 times the ULN	Permanently discontinue
Hepatitis/ HCC ^b	
 If AST/ALT is within normal limits at baseline and increases to more than 3 and up to 5 times the ULN If AST/ALT is more than 1 and up to 3 times ULN at baseline and increases to more than 5 and up to 10 times the ULN If AST/ALT is more than 3 and up to 5 times ULN at baseline and increases to more than 8 and up to 10 times the ULN 	Withhold dose ^c
	If AST or ALT increases to more than 10 times the ULN or total bilirubin increases to more than 3 times the ULN	Permanently discontinue
Hypophysitis	Grade 2 or 3 hypophysitis	Withhold dose ^a
	Grade 4 hypophysitis	Permanently discontinue
Adrenal Insufficiency	Grade 2 adrenal insufficiency	Withhold dose ^a
	Grade 3 or 4 adrenal insufficiency	Permanently discontinue

Adverse Reaction	Severity*	Dose Modification
Type 1 Diabetes Mellitus	Grade 3 hyperglycemia	Withhold dose ^a

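### The hepatic footnote in Appendix 2 does not say how its AST/ALT and bilirubin limits combine, and it contradicts the nivolumab hepatitis row in Section 6.1.3

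*Combined protocol and SAP*

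**What the plan says.** Three places give hepatic rules for the antibodies.

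- **Appendix 2, hepatic algorithm, starred footnote.** "I-O therapy may be delayed rather than discontinued if AST/ALT \leq 8 x ULN or T.bili \leq 5 x ULN". It sets two upper limits and no lower ones. The visible text does not say whether both must be met.
- **Section 6.1.3, nivolumab table, non-HCC hepatitis.** Permanent discontinuation applies at "AST or ALT more than 5 times the ULN or total bilirubin more than 3 times the ULN". Below that, the dose is withheld for AST/ALT above 3 and up to 5 × ULN, or bilirubin above 1.5 and up to 3 × ULN.
- **Section 6.1.3, ipilimumab table, hepatic row.** "Hepatic: Moderate elevations in transaminase (AST or ALT > 5 to ≤ 8 x ULN) or total bilirubin (> 3 to ≤ 5 x ULN)". The action is to withhold and to resume on resolution. The figures 8 and 5 appear here too, but as the tops of bands that also have a lower end.

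Two further sentences bear on how these texts relate. Section 6.1 says that for immune-related events, "if the management guidelines suggest delay or discontinuation, both nivolumab and ipilimumab should be held or discontinued". Appendix 2 describes its own status: "These general guidelines constitute guidance to the site Investigator".

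**The concern.** The footnote relaxes an instruction to discontinue. When two upper limits in such a relaxation are joined by *or*, meeting either one is enough, and exceeding one limit by any amount does not remove the exception while the other is met. Section 6.1.3 uses *or* in the opposite direction: there, exceeding either threshold triggers permanent discontinuation. The same pair of laboratory values can then be a delay in Appendix 2 and a permanent discontinuation in Section 6.1.3.

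What is at stake is consistent handling of hepatic events. Two sites with identical results could reach opposite decisions on further antibody treatment, each citing the protocol. That affects subject safety and makes exposure and discontinuation data harder to interpret in a small cohort (up to 18 subjects in the safety lead-in). Accrual halts after the lead-in, but subjects on treatment continue, so the text remains in use.

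**Working it through.** The plan gives no figure to reproduce. The check is one of logic, with A = AST/ALT and B = total bilirubin, both in multiples of ULN.

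Conditions, from the sections above:

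- Footnote as written: delay allowed if A ≤ 8 or B ≤ 5. It is lost only if A > 8 and B > 5.
- Same limits joined by *and* (a comparison only, not a proposed rule): delay allowed if A ≤ 8 and B ≤ 5.
- Nivolumab row: permanently discontinue if A > 5 or B > 3.
- Ipilimumab band: withhold if 5 < A ≤ 8 or 3 < B ≤ 5.

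| A | B | Footnote (*or*) | Footnote if *and* | Nivolumab row | In ipilimumab band, read literally? |
|---|---|---|---|---|---|
| 20 | 1 | delay allowed (B ≤ 5) | no exception | discontinue (A > 5) | no |
| 4 | 12 | delay allowed (A ≤ 8) | no exception | discontinue (B > 3) | no |
| 20 | 4 | delay allowed (B ≤ 5) | no exception | discontinue | yes, through B |
| 6 | 6 | delay allowed (A ≤ 8) | no exception | discontinue | yes, through A |
| 6 | 1 | delay allowed | delay allowed | discontinue (A > 5) | yes, through A |
| 9 | 6 | no exception | no exception | discontinue | no |

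Three things follow.

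1. **The connective matters.** The first two rows are the clean examples. The footnote allows delay, the nivolumab row discontinues, and neither value falls in an ipilimumab band.
2. **The connective is not the whole problem.** At A = 6, B = 1, the footnote and the nivolumab row disagree under *or* and under *and*. The same holds wherever A is above 5 and up to 8 with B ≤ 5, or B is above 3 and up to 5 with A ≤ 8.
3. **A wider grid agrees.** Take A = 4, 6, 8, 9, 12, 20 and B = 1, 2.5, 4, 5, 6, 12, which gives 6 × 6 = 36 pairs. The footnote as written withdraws the exception in 3 × 2 = 6 pairs (A of 9, 12 or 20 with B of 6 or 12) and keeps it in 36 − 6 = 30. With *and* it would keep it in 3 × 4 = 12. The two readings differ in 30 − 12 = 18 pairs, and the nivolumab row discontinues in all 18. Of the 12 pairs allowed under both readings, the nivolumab row discontinues in 10; the other two (A = 4 with B = 1 or 2.5) are withheld.

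These counts describe the chosen grid. They say nothing about how many subjects would have such values.

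**The case against.** The strongest reply is that the footnote is a minor guidance note that the protocol already overrides. Appendix 2 calls itself guidance, Section 5.6.1 says the algorithms should not replace medical judgement, and the footnote only permits delay. Section 6.1 lets investigators be more conservative and bases modifications on the event needing the greatest change. Section 6.1.3 permanently discontinues nivolumab for Grade 4 reactions, and Section 10.3.6 requires it for life-threatening immune-related ones. The box that the asterisk marks is not shown and may carry its own grade limit. The *or* may simply mean whichever test is raised.

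Much of this stands as a limit on the point, but it does not remove the contradiction. The greatest-modification sentence chooses among adverse events, not between two rules for one event. The nivolumab rows are themselves introduced as recommendations, and nothing ranks them against Appendix 2. The whichever-is-raised reading is plausible, but with no lower limits the footnote does not express it, and a normal bilirubin satisfies it as written.

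A reader might infer more than the documents support:

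- *That the protocol as a whole allows delay at any AST/ALT level.* It does not; the nivolumab row says otherwise.
- *That no dose table allows resumption above 8 × or 5 × ULN.* Read as literally as the footnote, the ipilimumab row admits 20/4 through bilirubin and 6/6 through AST/ALT.
- *That Section 6.1 gives Appendix 2 precedence, so that subjects would be re-exposed.* Section 6.1 only ties the two antibodies together.
- *That entinostat is included.* The footnote covers I-O therapy, which Section 5.6.1 identifies as nivolumab and ipilimumab; entinostat has its own rules in Section 6.1.1.
- *That the limits would almost never apply.* The documents give no frequencies.

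**Conclusion.** The point holds as a contradiction between sections. Taken literally, the footnote withdraws its exception only when both limits are exceeded, and it permits delay for values such as AST/ALT 20 × with bilirubin 1 × ULN, for which Section 6.1.3 permanently discontinues nivolumab. It also disagrees with the nivolumab row within its own limits, however they are joined. It should not be read as a uniform permission to resume treatment, or as evidence that any subject would be re-exposed.

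The conclusion rests on the visible footnote text. If the hidden box restricts it by grade or threshold, the range of affected values could be narrower; that cannot be checked. The correction is worth making because it is cheap and bears on the safety of subjects still on treatment. It does not touch the response-rate design or any calculated figure.

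**What to change.** 1. In the Appendix 2 footnote, state explicitly whether one or both limits must hold for the exception to apply.
2. Reconcile the footnote with the nivolumab and ipilimumab hepatic rows of Section 6.1.3, so that one set of laboratory values cannot lead to delay in one place and permanent discontinuation in another. Resolve the related difference between the two drug tables (AST/ALT above 5 and up to 8 × ULN; bilirubin above 3 and up to 5 × ULN) in the same edit.
3. State in Section 6.1 or 6.1.3 which text governs if the tables and Appendix 2 differ.

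Which clinical rule applies is for the sponsor-investigator and the drug supplier to decide. The cost is a corrected footnote, aligned table rows and a cross-reference, with notice to sites that still have subjects on treatment. No new procedures or data are needed.
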